The Principal Investigator, Lead Investigator and the MAI will be monitoring data collection and the study yearly or more often. Quality assurance (QA) will be performed by NIDA QA and NIAAA QA staff as indicated in the NIDA and NIAAA Quality Assurance Monitoring Plan on a schedule determined by the

Clinical Director. In addition to yearly monitoring of data collection, the Laboratory of Neuroimaging (LNI) utilizes a multi-layer study monitoring program. As a general practice, LNI lab staff records study procedures using a case report form (CRF) checklist on the day of each study. The study procedure checklist is completed on the day of study as well as within a few business days after the procedures were performed. Once a subject has completed all procedures per the protocol, a final study CRF monitoring log is completed for each participant. The CRF monitoring log captures that procedures were verified, data has been pushed to appropriate databases if necessary, questionnaire data entry verified if necessary, and the participant CRF folder monitoring log is signed by the LNI lab staff who verified the data. Following that process, each folder is monitored independently by other lab staff (i.e., post bac IRTA, clinical protocol coordinator, CRNP) as a final independent check that procedures were performed per protocol followed by signoff by the Principal Investigator.

b. Quality assurance plan

Quality assurance (QA) will be performed by the PI, as well as by an independent QA monitor, which according to established practice is considered sufficient for small, single-site trials, like the present project. The QA monitor for this study will have considerable expertise in clinical trials in drug dependence, but s/he will not work in the same section of the PI. Therefore, his/her role as QA monitoring will assure expertise and independence in the same time.

16. Reportable Events

Reportable events will be tracked and submitted to the IRB as outlined in Policy 801.

17. Alternatives to Participation

Participants neither receive nor forego treatment in order to participate in this study. The alternative, therefore, is not to participate.

18. Privacy

All research activities will be conducted in as private a setting as possible.

19. Confidentiality

a. For research data and investigator medical records

Medical records will be handled according to standard NIH Clinical Center policies, designed to prevent breach of privacy at a level considered sufficient for sensitive health care data. Investigators will be trained to respect the privacy and confidentiality of all participants including NIH employees and staff. Senior staff members (i.e., PI, MD, CRNP) will assure that all staff has completed the "Just in time" human subject's protection training course on "Biomedical- Vulnerable

Subjects-Workers/Employees" prior to engaging in recruitment of NIH employees. Privacy and confidentiality for NIH Employees will be adhered to the same as for other subjects. The certificate of confidentiality (CoC) that will be applied for this study will be used to resist demands for subject information as allowed by law. Staff will be reminded when an NIH employee has been recruited to use extra precautions so that identifying information will be protected. Confidentiality and information technology standards are in place at the NIAAA and NIDA intramural programs to protect electronic repositories of patient data as well as other clinical patient related material. It is reasonably expected that these safeguards will protect participants' medical and personal health information, ensuring their privacy.

Information obtained in the course of being screened for or participating in this protocol will become part of the patient's NIH medical record. This includes potentially sensitive information, such as results of urine tests that are positive for illicit drugs. Access to this information may be requested by third parties. Such access will not be granted without the explicit, written consent of the subjects. However, failure on the part of the subject to provide access to the information may in itself be to the disadvantage of the subject, e.g. in the case of a potential employer or insurer requesting the information. This situation will be made clear in the consent.

b. For stored samples

Samples and data will be stored using codes that we assign. Data will be kept in password protected computers. Samples will be kept in locked storage. Only study investigators will have access to the samples and data.

c. Special precautions

The Investigators are applying for a Certificate of Confidentiality (CoC) issued by NIH to further protect subject confidentiality.

20. Conflict of Interest

a. Distribution of NIH guidelines

NIH guidelines on conflict of interest have been distributed to all investigators.

b. Conflict of interest

There are no conflicts of interest to report.

c. Role of a commercial company or sponsor

There is no drug company involved.

21. Technology Transfer

This study now has two separate data transfer agreements (DTA's) in place under the following docket numbers:

1. AA DTA 22-11002: This DTA is between UPENN and NIAAA/LNI. We will send deidentified (coded) MRI imaging data for further analysis which includes: MRS and fMRI time series and associated data as well as craving data in response to alcohol cues from the fMRI scan sessions to our collaborator at UPENN for analyzation. UPENN will send back the results and we will match it back up to the subjects on our end.
2. AA DTA 22-11006: This DTA is between Zhejiang University, China, and NIAAA/LNI. We will send coded MRI imaging data for further analysis which includes: fMRI resting state time series and associated data as well as craving data in response to alcohol cues from the fMRI scan sessions to Zhejiang University China, for analysis. Zhejiang University will send back the results and we will match it back up to the subjects on our end.

22. Research and Travel Compensation

Volunteers will be compensated for time and research-related inconveniences, to the extent to which they complete them, as follows:

Procedures	Inconvenience Units	\$ Payment	Frequency	Total
Week 1 Study Procedures				
KD/SA Randomization Week	10	100	1	100
Genetics blood draw	1	10	1	10
Urine Drug Screen prior to MRI/NPT	1	10	1	10
Saliva Drug Screen prior to MRI/NPT	1	10	1	10
Urine pregnancy if female who can become pregnant prior to MRI/NPT	1	10	1	10
Ketone blood test #1 – obtained prior to start of KD/SA start	1	10	1	10
Ghrelin blood test #1 – obtained prior to start of KD/SA start	1	10	1	10
MRI session #1 (structure, functional reactivity, functional connectivity, MRS)	10	100	1	100
Neuropsychological Test Battery and Personality tests (NPT) including questionnaires Session #1	13	130	1	130

Sleep Profiler #1	10	100	1	100
Sleep Profiler #2	10	100	1	100
TMGENEActiv #1 (entire week of wear)	10	100	1	100
Ratings for Mood, Sleep, and Alcohol Craving	7	70	daily	total of 70
Daily urine ketone test	1	10	daily	total of 70
Ketone finger prick	1	10	Up to 5x/week	max of 50
Ketone blood test #2	1	10	1	10
Ghrelin blood test #2	1	10	1	10
Liver function, FFA platelets/coagulation blood test #1	1	10	1	10
Week #1 – Total Compensation up to				\$910

Week 2 Study Procedures

KD/SA Randomization Week 2	10	100	1	100
Urine Drug Screen prior to MRI	1	10	1	10
Saliva Drug Screen prior to MRI	1	10	1	10
Urine pregnancy if female who can become pregnant prior to MRI	1	10	1	10
MRI session #2 (structure, functional reactivity, functional connectivity, MRS)	10	100	1	100
Sleep Profiler #3	10	100	1	100
Sleep Profiler #4	10	100	1	100
Ratings for Mood, Sleep, and Alcohol Craving	7	70	daily	total of 70
Daily urine ketone test	1	10	daily	total of 70
Ketone finger prick	1	10	Up to 5x/week	max of 50
Ketone blood test #3	1	10	1	10
Ghrelin blood test #3	1	10	1	10
Liver function, FFA, platelets/coagulation blood test #2	1	10	1	10
Week #2 – Total Compensation up to				\$650
Week 3 Study Procedures				

KD/SA Randomization Week	10	100	1	100
Urine Drug Screen prior to MRI/NPT	1	10	1	10
Saliva Drug Screen prior to MRI/NPT	1	10	1	10
Urine pregnancy if female who can become pregnant prior to MRI/NPT	1	10	1	10
MRI session #3 (structure, functional reactivity, functional connectivity, MRS)	10	100	1	100
NPT including questionnaires Session #2 (Personality Measures will not be repeated)	13	130	1	130
Sleep Profiler #5	10	100	1	100
Sleep Profiler #6	10	100	1	100
TM GENEActiv #2 (entire week of wear)	10	100	1	100
Ratings for Mood, Sleep, and Alcohol Craving	7	70	daily	total of 70
Daily urine ketone test	1	10	daily	total of 70
Ketone finger prick	1	10	Up to 5x/week	max of 50
Ketone blood test #4	1	10	1	10
Ghrelin blood test #4	1	10	1	10
Liver function, FFA, platelets/coagulation blood test #3	1	10	1	10
Week #3 – Total Compensation up to				\$880
Potential Week 4 Study Procedures				
♦KD/SA Randomization Week	10	100	1	100
Week #4 – Total Compensation up to				\$100
Total Compensation to all subjects up to paid on discharge				\$ 2540
Telephone Follow-Ups				
Week 1 post discharge	1	10	1	10

Week 2 post discharge	1	10	1	10
Week 4 post discharge	1	10	1	10
Week 8 post discharge	1	10	1	10
Week 12 post discharge	1	10	1	10
Total Compensation for F-Ups				50
Total Compensation to all subjects up to paid on discharge				\$ 2590

♦ Note that if KD continues into Week 4, subjects will be compensated.

Compensation will be paid to subjects on day of discharge, and separately for each follow-up call. Compensation will be prorated for parts completed if subjects do not complete the study. If a subject is withdrawn from the study for non-compliance, he/she will be paid for procedures completed up to the point of withdrawal. If needed, subjects will be provided with a taxi paid for by NIH. *If needed, MRI/MRS scans may be repeated due to excessive head motion or equipment failure, for which participants will be paid an additional \$100 per MRI session. The maximum number of scans in the protocol is 5. If patients need to repeat other study procedures, they will be reimbursed for this according to the same inconvenience units for these procedures; e.g., \$100 for 1 night of sleep profiler, \$100 for GENActiv, \$10 per urine ketone test.

NIH employees or staff who participate during work hours must have permission from their supervisor. NIH employees or staff must either participate outside of work hours or take leave in order to receive compensation.

23. References

See end of document.

24. Attachments/ Appendices

a. Eligibility checklists

Uploaded to iRIS.

b. Recruiting advertisements

Uploaded to iRIS.

c. AUD medications list

Uploaded to iRIS for IRB review.

d. Eligibility Exclusion Medications checklist

Uploaded to iRIS for IRB review.

e. Study Day Medications checklist

25. Consent Forms

- AUD consent uploaded to iRIS

References

- 1 Volkow, N.D., et al., *Acute alcohol intoxication decreases glucose metabolism but increases acetate uptake in the human brain*. Neuroimage, 2013. **64**: p. 277-83.
- 2 Wang, J., et al., *Oxidation of ethanol in the rat brain and effects associated with chronic ethanol exposure*. Proc Natl Acad Sci U S A, 2013. **110**(35): p. 14444-9
- 3 Pawlosky, R.J., et al., *Alterations in brain glucose utilization accompanying elevations in blood ethanol and acetate concentrations in the rat*. Alcohol Clin Exp Res, 2010. **34**(2): p. 375-81.
- 4 Jiang, L., et al., *Increased brain uptake and oxidation of acetate in heavy drinkers*. J Clin Invest, 2013. **123**(4): p. 1605-14.
- 5 SAMHSA. *Substance Abuse and Mental Health Services Administration (SAMHSA). 2012 National Survey on Drug Use and Health (NSDUH)*. Available at: <http://www.samhsa.gov/data/NSDUH/2012SummNatFindDetTables/DetTabs/NSDUH-DetTabsSect2peTabs43to84-2012.htm - Tab2.71B>. 2012 [cited 2014].

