8. Presence of ferromagnetic objects in the body that are contraindicated for MRI of the head, fear of enclosed spaces, or other standard contraindication to MRI (self-report checklist).
9. Cannot lie comfortably flat on his/her back for up to 2 hours in the MRI scanner (self-report).
10. Body weight > 550 lbs. The MR scanner bed is tested to a weight limit of 550 lbs.
11. Milk or soy allergy (self-report).

Note that subjects will not be excluded on initial screening from enrollment onto this study if their breath alcohol test is positive; or if their urine test is positive for drugs. The following guideline will be followed for positive alcohol/drug screens on study procedure days:

- If an AUD subject's breath alcohol and/or urine drug screen test is/are positive on study days (i.e., within 24 hours before study procedures except for benzodiazepines during detox, including oxazepam [™Serax]), the procedures will be postponed and rescheduled to another day. If the urine drug screen is positive for THC-COOH, a saliva drug screen will be performed and subject may proceed with MRI/NPT procedures if saliva results for THC are negative. We will not place a limit on rescheduling study days.

4. Study Design and Methods

a. Study overview

This study includes an inpatient component and outpatient follow-up.

Patients are admitted to the Clinical Center (CC) for detoxification and treatment as usual (TAU) under protocol 14-AA-0181. Under the current protocol, patients will be randomized into a meal and shake plan consisting of either a standard American (SA) versus a ketogenic diet (KD). Patients will be given benzodiazepines only if withdrawal symptoms emerge while receiving either the KD or the SA diet. Subjects may be administered benzodiazepines only if withdrawal symptoms emerge. On day 2-6 after admission, all patients will undergo an MRI (brain structure, functional reactivity, functional connectivity and MRS) and will have a battery of neuropsychological tests (NP). Personality tests will be obtained during week 1 at the time of NP testing. The MRI scans will be repeated at 1 week intervals (Week 2 and 3). The Sleep Profiler device will be obtained 2X p/week in weeks 1-3. The ™GENEActiv (actigraphy) will be done for an entire week in weeks 1 and 3. The NP studies will be repeated coincident with the last MRI session. We will complete studies on at least 25 alcoholics with the ketogenic diet and 25 with the regular diet.

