Procedures	Week 1	Week 2	Weeks 3-4
KD/SA Randomization (solid food and shake) 3 snacks and 3 shakes p/day until stopped – up to 4 weeks while inpatient	x	x	x
Neuropsychological test battery (NPT)	x		x
Personality tests	x		
MRI Scan session (structure, functional reactivity, functional connectivity, MRS) ~ 3 hrs	x	x	x
Sleep Profiler	2x	2x	2x

TMGENEActive (actigraphy) – full week	x		X
Urine tests for ketones	Daily	Daily	Daily
Finger pricks for ketones	up to 5x	up to 5x	up to 5x
Blood tests for ketones and ghrelin	2x	1x	1x
Blood tests for fatty acids, liver function, platelets and coagulation	1x	1x	1x

Time points are targets, and the order can be adjusted for practical considerations during the inpatient stay.

Upon discharge from the NIH CC, participants in the study will be followed up for 3 months. For this purpose, we will call the participants by phone at weeks 1, 2, 4, 8 and 12 to ask questions about relapse and sobriety. This will take about 5 minutes or less. The following questions which are from the Alcohol Timeline Follow Back (ATFB) will be asked during the follow up:

- i. In the last 7 days, did you drink any alcohol?; Y ___ N ___
- ii. If yes we then ask “On what days did you drink”?; and
- iii. How much did you drink?

b. Recruitment

Participants will be recruited through referrals from the NIH Volunteer Office, the Patient Recruitment and Public Liaison (PRPL) Office, the NIAAA Intramural Research Program screening protocol 14-AA-0181 and through ResearchMatch.org and www.craigslist.com.

Participants (including NIH employees with an AUD) will also be recruited by word of mouth and through IRB-approved local advertisements. There will be no direct solicitation of employees by supervisors or coworkers. These will include: (1) Flyers posted on NIH campus, campuses of universities and colleges, public places and public transportation services in the greater Washington DC area; (2) Advertisements in electronic and printed local media (newsletters, websites including www.niaaa.nih.gov/join-study#, researchstudies.drugabuse.gov, newspapers including the Baltimore Beat, Baltimore Sun, the Beacon, Washington City Paper, Streetsense, the Express, craigslist.org, NIH and other local email distribution lists), following IRB approval, (3) through substance abuse treatment programs of clinics (e.g. Caron Treatment Facilities).

ClinicalTrials.gov may also represent a source of recruitment.

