age will be used to determine how many calories are provided to each participant. While on the KD/SA diet, patients are limited to drink non-caloric drinks (water, diet soda, coffee and tea without milk or sugar). In addition to the diets, MRI/fMRI/MRS scans, genetic tests, self-report ratings, motor activity, sleeping behavior, NP testing and personality measures will be obtained in all participants. The first MRI session and the first NP testing will be performed within the first 2-6 days of admission. The MRI sessions will be repeated on a weekly basis (second and third week of hospitalization; the later corresponding to the last week of their inpatient stay) and the NP testing will be repeated during the third week of hospitalization. MRI scanning session and NP tests are described below and are for research purpose only.

During the inpatient period, participants will be periodically monitored for signs of withdrawal and evaluated for mood, sleep and alcohol cravings. Compliance with diet adherence (KD or SA) will be closely monitored during the hospital stay using daily urine tests.

After the final MRI sessions, the study diets are discontinued and the individual blind will be broken on a per subject basis. If KD is discontinued this will be done by slowly increasing the levels of carbohydrates to the diets of the SA group [68]. The levels of carbohydrates in the control group remains constant throughout the study, but patients are still blind to treatment group.

Participants will then be released at about 3-4 weeks from the Clinical Center and will have a 3 month follow up period under this protocol which is discussed below in section 4.d.12 *Follow-Up*.

1. Ketogenic Diet (KD) / Standard American (SA) Snacks and Shakes: Participants will be randomized to a meal plan of either a ketogenic diet (KD) or standard American (SA) diet at the time they sign the consent (day 1 or 2 of admission). For each meal at breakfast, lunch and dinner, the diets will consist of SA meal (carbohydrate rich) or KD meal depending on treatment randomization. Compliance tests are done daily with urine tests measuring ketone levels by an independent person (BSN RN) [69], results of which are retained. To ensure that the diet is double blind in both the outpatient and inpatient phases, solid snacks are always ketogenic and shakes are either KD or SA.

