In this way, all participants will remain in the study for at least the first 7 days and will be included in the analysis on the effects of KD on withdrawal symptoms, benzodiazepine use, MRI and NPT within the first 7 days. After 7 days participants may be withdrawn from the study based on non-compliance to the diet.

4. **MRI scans:** MRI evaluations of the brain are being performed at 3Tesla (3T) (Siemens Prisma). These MRI scans are performed on FDA-approved scanners with approved radiofrequency coils, and their use conforms to the corresponding FDA labels. The MR scanner is being used in normal mode (not research mode) using the following pulse sequences: magnetization-prepared rapid gradient-echo (MPRAGE), Prospective Acquisition Correction (3D PACE), diffusion tensor imaging (DTI), echo-planar imaging (EPI), arterial spin-labeling (3D ASL), and Magnetic Resonance Spectroscopy (MRS).

MR acquisition: A high resolution T1-weighted magnetization-prepared rapid gradient-echo pulse sequence (MP2RAGE) will be used to map brain structure with high spatial resolution and excellent gray-white contrast and to map T1 relaxation in the brain. DTI, an MRI technique that can quantify isotropic and anisotropic water diffusion, will be used to map fractional anisotropy and the apparent diffusion coefficient, and to assess the structural connectivity of the brain. ASL, an MRI-based method that utilizes blood as an endogenous tracer and provides noninvasive quantification of tissue perfusion, will be used to map CBF in the resting state. BOLD-weighted functional images will be collected to measure brain activation and to map functional connectivity. *Brain activation paradigms:* We will use passive viewing of neutral, food and drug related pictures [40 pictures per category; the neutral, alcohol and food pictures will be selected from freely available online and in-house collections) [71, 72]. Pictures will also be rated for characteristics such as valence, liking and wanting. The stimuli are presented to the subjects on an MRI-compatible 32-inches LCD screen synchronized with the MR acquisition using an MRI trigger pulse.

We will use the delayed discounting task (DDT) to evaluate effects on self-regulation. The DDT task has been used extensively [for review see [73]. It

allows measurement of BOLD response to immediate reward responses versus responses to delayed rewards.

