Pearson correlation will be used to test **Hypothesis 5**, “acetone and β -hydroxybutyrate concentration in the anterior cingulate and frontal white matter will increase linearly as a function of time week #1, #2 and #3”. Assuming $\alpha = 0.05$ and $\beta = 0.2$, the proposed sample sizes will allow us to detect statistically significant correlation coefficients, $r > 0.6$.

From our past experience with neuroimaging of patients with AUD, it is expected that, even with careful screening and preparation, approximately 50% of participants will not be able to complete protocols with neuroimaging like the current one being proposed. Thus, we are proposing to recruit 100 participants in order to complete studies in 50 of them (25 on KD and 25 on SA diet).

* We expect that more than 25 patients per group will finish the first week of KD and its assessment of withdrawal symptoms, and will therefore include all patients who finished these assessments to test Hypothesis 1.

11. Human Subjects Protection

a. Subject selection

Adults who fulfill the eligibility criteria will be included, regardless of race, ethnicity, sex, or religious affiliation. We predict the racial composition is approximately 60% Caucasian, 35% African American, and remaining 5% proportion of Asian or other. We predict the Hispanic ethnicity to be approximately 25%. On the same basis, the expected breakdown is 70% male and 30% female. The age range of 18 years and older will provide a sample size that hits our target inclusion criteria of a minimum of 5 year of heavy drinking history.

b. Justification for exclusion of children

Children are excluded since it is unlikely that they will meet the ten-year criteria of heavy drinking required for the study.

c. Justification for exclusion of other vulnerable subjects

Vulnerable populations such as those who lack capacity to consent, are also excluded due to the likely inability to follow instructions for tasks to be performed during diet (KD or SA meal/shake protocol) randomization, MR scans and NP

testing. We also exclude individuals with major psychiatric disorders since this may affect brain function and structure, and may influence study results.

d. Justification for sensitive procedures

N/A

e. Safeguards for vulnerable populations and sensitive procedures

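### Hypothesis 5 uses nominal week as its time variable although session dates can drift, so it measures time on diet imprecisely; actual days since diet start would serve better

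*Combined protocol and SAP*

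**What the plan says.** **Time variable.** Section 10.b plans a Pearson correlation for Hypothesis 5: acetone and β-hydroxybutyrate in two brain regions "will increase linearly as a function of time week #1, #2 and #3".

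**Session timing.** Section 4.e states: "The first MRI session and the first NP testing will be performed within the first 2-6 days of admission". MRI is then repeated weekly. Below the schedule table, Section 4.a adds: "Time points are targets, and the order can be adjusted for practical considerations during the inpatient stay".

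**Postponement.** Under Section 3.c, if the breath alcohol or urine drug test on a study day is positive, "the procedures will be postponed and rescheduled to another day", and "We will not place a limit on rescheduling study days". Two exemptions narrow the trigger. Positive results do not count "except for benzodiazepines during detox", and after a THC-positive urine the "subject may proceed with MRI/NPT procedures if saliva results for THC are negative".

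**Early analysis.** Section 4.e.3 keeps every participant in the study for at least a week. Of these participants it says that they "will be included in the analysis on the effects of KD on withdrawal symptoms, benzodiazepine use, MRI and NPT within the first 7 days".

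Section 10 gives no analysis window and no rule for a session done outside its target days.

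**The concern.** Hypothesis 5 concerns a rise in brain ketones with time on the diet, so the relevant scale is days since the diet began. Week number replaces that scale with three equally spaced labels. Any gap between label and actual diet day is measurement error in the time variable, and it weakens the correlation that the test is meant to detect.

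Some drift is foreseeable. A drug-positive urine does not bar entry, and mild or moderate other substance use disorders are allowed (Section 3.c). The two exemptions do not cover other drugs or THC-positive saliva.

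There is also a smaller inconsistency. A postponement without a stated maximum cannot guarantee that every participant has a first MRI and NP session inside the first 7 days, as Section 4.e.3 says.

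**Working it through.** **The plan's own figure.** The documents give no figure for the precision of the time variable. The nearest is the detectable correlation for Hypothesis 5, r > 0.6. With 25 patients, α = 0.05 two-sided and 80% power, Fisher's z gives tanh((1.960 + 0.842)/√22) = 0.535, so 0.6 is not reproduced. That is a separate discrepancy, and nothing below depends on it.

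**Inputs from the documents**
- First session on day 2-6 of admission, later sessions at weekly intervals (Sections 4.a, 4.e).
- Randomisation to diet on day 1 or 2 of admission (Section 4.e.1).

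**Assumptions not in the documents**
- Each day in 2-6 is equally likely, and so is a diet start on day 1 or 2.
- A share q of patients, 10-30%, is delayed by 3, 4, 5, 6 or 7 days with equal chance (mean 5, mean square 27).

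**No postponement.** Let k = 1, 2, 3 be the week number, with variance 2/3. Diet day is 7k plus a patient-specific offset.
- Variance from week: 49 × 2/3 = 32.67.
- Variance from offset: 2 (first-session day) + 0.25 (diet start) = 2.25.
- Total: 34.92.
- Correlation of week with diet day: √(32.67/34.92) = 0.967.

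**Only session 1 is delayed**
- Covariance of week and diet day: (14 − 5q)/3.
- Variance of diet day: 34.92 − 23.33q + 9q − (5q/3)².
- Correlation: covariance / √(2/3 × variance).

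**All three sessions are delayed equally**
- Covariance: 14/3.
- Variance: 34.92 + 27q − 25q².

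| q | Session 1 only: cov; var; correlation | All sessions: cov; var; correlation |
|---|---|---|
| 10% | 4.50; 33.46; 0.953 | 4.67; 37.37; 0.935 |
| 20% | 4.33; 31.94; 0.939 | 4.67; 39.32; 0.912 |
| 30% | 4.17; 30.37; 0.926 | 4.67; 40.77; 0.895 |

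**Share due to rescheduling.** Measured against 0.967, the loss from delay is:
- session 1 only: 1 − 0.953/0.967 ≈ 1.5% to 1 − 0.926/0.967 ≈ 4%;
- all sessions: 1 − 0.935/0.967 ≈ 3% to 1 − 0.895/0.967 ≈ 7%.

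The remaining 3% or so (1 − 0.967) comes from the ordinary day 2-6 spread and the diet start, without any positive screen.

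**Effect on Hypothesis 5.** If the true relation is linear in diet day with correlation r, the correlation with week is r times the tabulated value. For r = 0.60 that gives 0.60 × 0.967 = 0.58 with no delay, 0.57-0.56 if session 1 alone slips, and 0.56-0.54 if all sessions slip.

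**First-7-days analysis.** Of the 5 × 5 = 25 equally likely combinations of planned day (2-6) and delay (3-7), 19 sum to more than 7. So 76% of delayed first sessions would fall after admission day 7. With 10-30% delayed, that is 0.76 × 2.5 ≈ 2 to 0.76 × 7.5 ≈ 6 of 25 patients.

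**The case against.** Much of the case on the other side stands.

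- **A week-2 scan entered as week 1.** A reader might infer that the plan does this. No section says so; the plan is silent on out-of-window sessions. For the early analysis, the first-7-days wording in Section 4.e.3 points the other way.
- **Session number as the time variable.** Section 10 never uses it. Numbered MRI sessions appear only in the compensation table of Section 22.
- **A shortened interval between first and last scan.** A reader might infer that a 7-day delay cuts a 14-day interval to 7. That requires later sessions to stay fixed. The schedule table places the last MRI in weeks 3-4, Section 4.d gives a stay of about 4 weeks, and Section 22 budgets a fourth week. A first session on day 6 + 7 = 13 could be followed by sessions on days 20 and 27. Compression is possible, because Section 4.e links the third MRI to the third week and allows release at about 3 weeks, but it is not forced. The case for changing the Hypothesis 2-4 models is therefore not made.
- **Target versus window.** A target with permission to reschedule is not in itself a contradiction, and the absence of a limit may refer to the number of reschedulings. On either reading no maximum delay is stated.
- **Frequency.** The 10-30% is assumed. The two exemptions and inpatient status should keep it down.
- **Bias.** The screening rule is the same in both arms, so the documents show noise, not a biased diet comparison.

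These points do not alter the fact that Hypothesis 5 is stated in nominal weeks while session dates may vary.

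**Conclusion.** The point holds as a minor improvement to a stated method. Nominal week measures time on diet imprecisely: it correlates about 0.97 with diet day if every first session falls in its day 2-6 target. Under the assumed 10-30% of patients delayed 3-7 days, this becomes 0.95-0.93 if only the first session moves, or 0.94-0.90 if all move. Rescheduling thus adds roughly 1.5-7% attenuation to the Hypothesis 5 correlation. The true size is unknown because the documents give no rate of positive screens. The calculation also assumes a linear rise in diet days, evenly spread first-session days and a diet start on the day of randomisation. The wording on postponement, the day 2-6 target and the first-7-days analysis needs reconciling, but this does not threaten the trial's main comparison.

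**What to change.** 1. In Section 10.b, replace week number with actual days since diet start as the time variable for Hypothesis 5.
2. Apply the first-7-days limit in Section 4.e.3 by actual date, and state the day from which it is counted. A first MRI or NP session done later is analysed at its true day and treated as missing for the week-1 summary.
3. Reconcile three statements: no limit on rescheduling (Section 3.c), the day 2-6 timing of the first session (Section 4.e), and the inclusion of all participants in the first-7-days MRI and NPT analysis (Section 4.e.3).

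The cost is wording. Procedures are logged on case report forms on the day (Section 15.a), and daily ketone testing is already timed from diet start (Section 4.e.1), so no new data are needed. The downside is that a few patients leave the early imaging summary: about 2 to 6 of 25 under the assumed delays.
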